## **ABSTRACT**

**Purpose:** This is a phase I study to establish safety data of hypofractionated stereotactic radiotherapy (SRT) in patients with hepatocellular carcinoma.

**Eligibility criteria:** Patients must have pathologically confirmed hepatocellular carcinoma with at least one tumor with a maximum diameter of  $\leq 8$  cm and must have Karnofsky performance status  $\geq 60\%$  and a life expectancy of at least 12 weeks. Patients must be  $\geq 19$  years of age and able to give written informed consent prior to initiating treatment. Previous systemic chemotherapy or non-radiation local therapy (such as surgery, hepatic arterial therapy, chemoembolization, radiofrequency ablation, percutaneous ethanol injection or cryoablation) is allowed.

**Interventions:** All patients who have had successful implantation of a liver marker will undergo a 4D CT scan for planning SRT. Following transfer to the treatment planning system, the CT scan may be correlated by imaging fusion with MRI for contouring integrated tumor volume (ITV). The planning target volume (PTV) will be defined as ITV plus individualized margins which are determined by a 4D CT scan. Novalis with 6MV photons will be used for imaging guided SRT. Cohorts of 3-6 patients will receive SRT at daily doses of 8, 10, 12, 14 Gy within 2 weeks. The starting daily dose level will be 10 Gy. The marker will be localized by orthogonal X-ray to ensure reproducibility. A continuous respiratory gating will be accomplished with ExacTrac Adaptive Gating system if the required planning target margin is larger than 1 cm based on the 4D CT data.

### **Evaluation:**

- 1) Liver, right kidney and small bowel toxicity will be evaluated according to CTCAEv3.0
- 2) Tumor response will be accessed by tumor marker (AFP), CT and MRI scans

**Follow-up:** As part of standard of care, all patients will have a follow-up visit 1 month after SRT and every 3 months for 1 year and every 3 to 6 months indefinitely. The study follow-up will coincide with these visits. The last study follow-up visit will be 4 months after the completion of radiation therapy.

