## Section 1.0 Objectives

- 1.1 Primary Objective:
  - 1.1.1 The safety of hypofractionated stereotactic radiotherapy in patients with advanced hepatocellular carcinoma.
    - 1.1.1.1 Record SRT related liver, right kidney, small bowel toxicity according CTCAEv3.0
- 1.2 Secondary Objective:
  - 1.2.1 The maximum tolerable SRT dose.
  - 1.2.2 Objective tumor response rate.
    - 1.2.2.1 Report the percentage of tumor size change on CT
    - 1.2.2.2 Report the percentage of intensity change on MRI
    - 1.2.2.3 Report the percentage of change in AFP
  - 1.2.3 The value of 4D CT in liver cancer planning
    - 1.2.3.1 Report extent of liver motion three dimensionally
    - 1.2.3.2 Report the percentage of patients requiring breath gating because of the amplitude of organ motion exceeding 1 cm in any dimension.
  - 1.2.4 The value of breath gating in liver cancer SRT
    - 1.2.4.1 Report the success rate of breath gating
    - 1.2.4.2 Report the percentage of treatment time prolongation secondary to the gating.

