5.2.4 Treatment Delivery: The planning data containing the coordinates of tumor isocenter, the external infrared markers, and the implanted marker are transferred to the ExacTrac Adaptive Gating platform. The daily initial positioning will be performed using lasers and skin marks. The target isocenter will be verified on daily x-rays. If the patient meets the criteria of breath gating, treatment delivery is accomplished using the ExacTrac Adaptive Gating in combination with Novalis. External infrared markers attached to the patient's skin are used to determine the breathing pattern. The respiratory moving target is positioned, under infrared and x-ray guidance to a defined point within the patients' end expiratory breathing cycle. The gating reference level will be defined to evaluate target motion due to respiration. The size of beam-on window will be determined based on the target motion as detected by the 4D CT scan.

5.3 The study follow-up will coincide with the standard of care follow-up visits which will be 1 and 3 months after the completion of SRT. None of the tests or procedures is

performed more frequently than would be considered clinically standard. No procedures would be done exclusively for research purposes.

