#### 5.4 Toxicity:

- 5.4.1 Implantation of a liver marker: The side effects of implantation will be similar to the needle biopsy of liver tumor and the stent placement including but not limited to tumor seeding, foreign body, infection, bleeding, pain at local area, and dislocation of the marker.
- 5.4.2 SRT: Short term side effects include but not limited to skin reaction, local hair loss, fatigue, abdominal pain, nausea, vomiting, diarrhea, increasing liver function abnormality, GI bleeding or perforation which may require surgical intervention. Long term side effects are less likely to occur but if they do occur are more likely to be permanent. They include local hair loss, liver function abnormality, diarrhea, small bowel obstruction which may require surgical intervention, spinal cord injury which could result in paralysis, kidney function abnormality.

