## Section 7.0 Study Parameters

### 7.1 Laboratory/imaging Studies:

Parameter	Baseline	Pre- and post-SRT therapy	Post-Treatment Follow-up
History	X	X b	a
Physical examination	X	X b	a
Weight	X	X	a
Vital signs	X	X	a
Performance status (Karnofsky)	X	X	a
CBC, differential, platelet count	X	X Post- SRT	a
Comprehensive metabolic panel (including bilirubin, alk phos, AST, ALT, )	X	X Post- SRT	a

Fill out pain assessment card	X	X Post-SRT	a
AFP	X	X post-SRT	a
PT, PTT, INR	X	X Post-SRT	a
CT	X	X simulation	
MRI	X	X Post-SRT	a
Serum pregnancy test	prn		

*a - will be done at one month and 3 months after the completion of SRT*

*b – A brief physical exam and history will be performed*

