#### Endpoints

Toxicity will be graded by NCI Common Toxicity Criteria (CTC Version 3.0). Due to delayed toxicities attributable to radiotherapy, all toxicities observed within 1 month after SRT will be scored. DLT is defined as any of following toxicities, that is possibly, probably or definitely related to SRT occurring within 30 days from the start of treatment:

- a) grade 4 or 5 hepatic
- b) grade 4 or 5 gastrointestinal
- c) grade 4 or 5 thrombocytopenia
- d) grade 4 hepatic liver enzyme elevations persisting for  $\geq 5$  days
- e) any adverse event requiring interruption of therapy by  $\geq 2$  weeks (14 calendar days). This does not include patient desire to discontinue therapy. It does include failure for thrombocytopenia to improve to a level of 80 requiring interruption of therapy.
- f) Any grade 5 treatment-related adverse event

The MTD of SRT is defined as the highest dose level at which no greater than 2 DLT is observed in 6 patients.

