## Appendix II

### Schedule of Activity

	Screening/Baseline	Liver Marker Implant Procedure	1-7 Days Post Implant	SRT planning,	Start SRT	End SRT	1 month Post SRT	3 Months Post SRT
History & Physical	x		x	x	x	x	x	x
CT abdomen/pelvis	x	x		x				
MRI abdomen/pelvis	x			x				x
biopsy	x							
Inclusion/Exclusion	x							
Informed consent	x							
CT or U/S guided marker implant		x						
AFP	x			x			x	x
CBC with diff	x		x	x			x	x
INR	x							
complete chemistry pannel	x		x	x			x	x
Chest X-ray or Chest CT	x							
Record adverse events		x	x	x	x	x	x	x

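### Adverse-event recording is not scheduled beyond 3 or 4 months and 10.1 states a 1-month scoring window; clarifying that window and using existing visits to 12 months would cheaply improve the safety report

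*Combined protocol and SAP*

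**What the plan says.** **What is to be measured.** Section 1.1.1.1, under the primary safety objective, reads "Record SRT related liver, right kidney, small bowel toxicity according CTCAEv3.0". Section 5.4.2 adds "Long term side effects are less likely to occur but if they do occur are more likely to be permanent" and lists small bowel obstruction and abnormal liver and kidney function among these effects.

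**Routine visits.** The abstract provides that "all patients will have a follow-up visit 1 month after SRT and every 3 months for 1 year", and then every 3 to 6 months without an end date.

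**Study visits.** The same paragraph of the abstract says "The last study follow-up visit will be 4 months after the completion of radiation therapy". Section 5.3 ties study follow-up to "standard of care follow-up visits which will be 1 and 3 months after the completion of SRT", and the footnote in 7.1 says the post-treatment assessments "will be done at one month and 3 months after the completion of SRT".

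**Adverse-event recording.** The only explicit schedule is the Appendix II row "Record adverse events". It is marked from the marker implant to the last column, 3 months after SRT.

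**Scoring and analysis.** Section 10.1 (Endpoints) says "Due to delayed toxicities attributable to radiotherapy, all toxicities observed within 1 month after SRT will be scored". The next sentence defines dose-limiting toxicity (DLT) on a separate clock, 30 days from the start of treatment. Section 10.4 tables toxicity by dose level and gives no time window.

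**Other capture.** Section 9.2 (serious events to the Scientific Review Committee) and section 9.3 (general toxicity follow-up and recording) carry no end date.

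**The concern.** There are two gaps, of different kinds.

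The first is in wording. Events between month 1 and the last study visit are recorded under Appendix II, but the only scoring window the plan states ends at 1 month. An analyst who applied 10.1 literally could leave 3-month events out of the primary safety table. The sentence cites delayed toxicity as its reason, yet sets a window shorter than the recording schedule.

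The second is in design. The plan names late effects in the organs of its primary objective, and the patients keep coming to clinic, but no adverse-event recording is scheduled at those later visits. A bowel obstruction or a decline in liver or kidney function at, say, month 7 might be known to the clinic or the review committee. Whether it reached the safety report would depend on ad hoc reporting, and the report would not show how many patients at that dose were still being observed.

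**Working it through.** **1. Time windows side by side**

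| Source | Last point |
|---|---|
| 10.1, scoring sentence | 1 month after SRT |
| 5.3, 7.1 footnote, Appendix II | 3 months after SRT |
| Abstract, last study visit | 4 months after SRT |
| 10.4, table by dose level | none stated |
| 9.2, 9.3 | none stated |
| Abstract, routine visits | every 3 months to 1 year, then open-ended |

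The documents do not reconcile 3 with 4 months. Counting 3 months from the 1-month visit would explain it. Within the first year, 12 − 4 = 8 to 12 − 3 = 9 months have routine visits but no scheduled recording.

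**2. The plan's own figures.** The plan gives no figure on late toxicity. Its design figures reproduce and are untouched by this point: maximum enrolment is 3 × 6 + 10 = 28. With escalation on at most 1 DLT in 6, the probability of not escalating at a 35% DLT rate is 68.1% (stated: at least 68%), and of escalating at 20% it is 65.5% (stated: 66%).

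**3. How many patients are involved (illustration).** The documents give no onset times and no survival figure for this population. Assume exponential survival from the end of SRT, S(t) = 2^(−t/m). Medians m of 7.9 and 10.7 months come from the drug trial cited in section 2.0 (Systemic Therapy), and m = 6 is my less favourable case. Patients at the maximum tolerable dose (MTD): 6 + 10 = 16. Patient-months from month a to 12 are 16 × (m/ln 2) × [S(a) − S(12)].

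| | m = 6 | m = 7.9 | m = 10.7 |
|---|---|---|---|
| Alive of 16 at 3 months | 11.3 | 12.3 | 13.2 |
| Alive of 16 at 4 months | 10.1 | 11.3 | 12.3 |
| Alive of 16 at 12 months | 4.0 | 5.6 | 7.4 |
| Alive of 6 at 12 months | 1.5 | 2.1 | 2.8 |
| Patient-months, month 4 to 12 | 52.6 | 64.8 | 77.1 |
| Patient-months, month 3 to 12 | 63.3 | 76.5 | 89.8 |

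Ceiling, if nobody died: 16 × 8 = 128 to 16 × 9 = 144 patient-months.

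**4. What the late data could show.** With 0 events in n patients, the one-sided 95% upper limit is 1 − 0.05^(1/n).

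| n | 2 | 3 | 6 | 7 | 16 (ceiling) |
|---|---|---|---|---|---|
| Upper limit | 78% | 63% | 39% | 35% | 17% |

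If 40% of the 28 patients could be followed (assumed), late-event rates of 5%, 10% and 20% (assumed) would give 28 × 0.4 × rate = 0.6, 1.1 and 2.2 expected events.

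**5. Work added, for 28 patients.** If study follow-up ends at 4 months, the routine visits left in the year are at 7 and 10 months: 28 × [S(7) + S(10)] = 21.3, 26.8, 32.4 for the three medians. If it ends at 3 months, they are at 6, 9 and 12 months: 28 × [S(6) + S(9) + S(12)] = 30.9, 39.0, 47.5. Ceiling with no deaths: 28 × 2 = 56 to 28 × 3 = 84.

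**The case against.** The strongest case against has four parts.

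*Later events are not excluded.* A reader might infer that events after month 3 or 4 will not enter the toxicity table, or that they have no denominator. The documents do not support either. Sections 9.2, 9.3 and 10.4 carry no end date, 9.3 provides for nurse contact and faxed outside laboratory results, and the number treated at each dose level is known. The 10.1 sentence does not itself forbid scoring later events. What remains is narrower: late recording is unscheduled, and the number still under observation is not tracked.

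*The cut-off is deliberate.* The abstract names the longer routine schedule and sets the last study visit at 4 months in the same paragraph. That suits a dose-finding trial requiring a life expectancy of only 12 weeks. This stands: the cut-off is a design choice, not an error.

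*Harm is not shown.* Section 5.4.2 calls long-term effects less likely and gives no onset times. The background in section 2.0 cites a conformal series without late liver toxicity and early studies with little late normal-tissue damage. This stands too; the share of events missed cannot be computed.

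*The yield is small.* Few patients survive to 12 months. Laboratory panels are scheduled only to month 3, so grading later liver and kidney function would rest on whatever routine tests exist. Cirrhosis, progression and later therapy blur attribution. All of this limits the 12-month extension. It does not touch the month 1 to 3 or 4 ambiguity, where the events are already collected.

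**Conclusion.** The point holds as a cheap improvement in two parts. The firmer part is the wording of 10.1 and 10.4. The likely intent is that the 1-month sentence serves DLT assessment, since it stands beside that definition, but the text does not say so, and a literal reading conflicts with recording at 3 months. The second part is optional in character: systematic, descriptive capture of late events from visits that already take place.

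Under the assumed medians, about 10 to 13 of the 16 MTD patients are alive when scheduled recording stops and about 4 to 7 at 12 months. Some 53 to 90 patient-months would gain scheduled recording. These counts are illustrative: the medians come from a Child-Pugh A drug trial, whereas this trial admits Child-Pugh A and B with a target lesion of at most 8 cm, so true survival could lie on either side. The gain is counts with the number observed, not precise rates.

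A reader might also infer that the follow-up length undermines the DLT rule or the choice of dose. Nothing here shows that; escalation and expansion decisions are unaffected.

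**What to change.** (a) State in 10.1 and 10.4 that the 1-month window applies to DLT assessment only. State also that all recorded SRT-related toxicity, including at the 3- or 4-month visit, is graded and tabled by dose level. This costs one or two sentences.

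(b) As a low-cost descriptive addition, amend the abstract, 5.3 and Appendix II so that grade 3 or higher SRT-related events (CTCAE v3.0) are recorded from existing routine visits through 12 months or death. Recording should continue after removal for progression or DLT (5.6) unless consent is withdrawn. Report counts in 10.4 by dose level, with the number under observation at each visit.

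Leave the DLT definition, escalation timing and sample size unchanged.

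The cost of (b) is protocol wording, matching consent wording if needed, and abstraction of two or three routine visits per survivor: about 21 to 47 in total under the assumed medians. No patient, visit or test is added. The downsides are a late-toxicity report 8 to 9 months later, some records possibly held by community oncologists (4.1), incomplete laboratory data, difficult attribution and very sparse data.

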## Section 1.0 Objectives

- 1.1 Primary Objective:
  - 1.1.1 The safety of hypofractionated stereotactic radiotherapy in patients with advanced hepatocellular carcinoma.
    - 1.1.1.1 Record SRT related liver, right kidney, small bowel toxicity according CTCAEv3.0
- 1.2 Secondary Objective:
  - 1.2.1 The maximum tolerable SRT dose.
  - 1.2.2 Objective tumor response rate.
    - 1.2.2.1 Report the percentage of tumor size change on CT
    - 1.2.2.2 Report the percentage of intensity change on MRI
    - 1.2.2.3 Report the percentage of change in AFP
  - 1.2.3 The value of 4D CT in liver cancer planning
    - 1.2.3.1 Report extent of liver motion three dimensionally
    - 1.2.3.2 Report the percentage of patients requiring breath gating because of the amplitude of organ motion exceeding 1 cm in any dimension.
  - 1.2.4 The value of breath gating in liver cancer SRT
    - 1.2.4.1 Report the success rate of breath gating
    - 1.2.4.2 Report the percentage of treatment time prolongation secondary to the gating.

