5.2.3 Localization, Immobilization and Simulation: A body-fix bag will be used for treatment simulation and delivery. Infrared markers will be attached to the patient's chest and abdomen in suitable positions to yield a good breathing signal. A 4D CT scan of abdomen will be performed for treatment planning. Treatment Planning: Following transfer to the treatment planning system, the CT scan may be correlated by imaging fusion with a MRI scan for contouring tumor volume. Integrated tumor volume (ITV) will be generated. The planning target volume (PTV) is defined as ITV plus individualized margins, which will be determined by a 4D CT scan. The uniformity requirement will be +10% -5% of the total dose at the prescription point within the tumor volume. The IMRT may be used if there is a benefit of decreasing tissue complications. The dose to the kidney will require careful monitoring and kidney volumes must be defined on simulation fields. The percent of total kidney volume (defined as the sum of the left and right kidney volume) receiving 15 Gy (3 Gy per fraction) should be required to be less than 35% of the total kidney volume. The maximum dose to any point within the spinal cord should not exceed 15 Gy (3 Gy per fraction). At least 700 ml or 35% of normal liver (entire liver minus cumulative GTV) should receive at total dose less than 15 Gy (3 Gy per fraction). The maximum point dose to the stomach or small bowel except duodenum should not exceed 80% of prescription dose. An isodose distribution of the treatment at the central axis indicating the position of kidneys, liver and spinal cord is required. The treatment plans should be optimized using dose volume histograms of any irradiated vital organ.

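### Sections 9.3 and 10.1 give different answers on whether a grade 4 kidney event, in an organ named for the primary safety record, is a dose-limiting toxicity

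*Combined protocol and SAP*

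**What the plan says.** The primary objective in Section 1.1.1 is general: "The safety of hypofractionated stereotactic radiotherapy in patients with advanced hepatocellular carcinoma". The item beneath it, 1.1.1.1, is narrower: "Record SRT related liver, right kidney, small bowel toxicity according CTCAEv3.0". The Evaluation part of the abstract repeats the three organs: "Liver, right kidney and small bowel toxicity will be evaluated according to CTCAEv3.0".

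Section 10.1 (Endpoints) has a wider recording scope: "all toxicities observed within 1 month after SRT will be scored". Its DLT list is organ-specific in items (a) to (d): "grade 4 or 5 hepatic", "grade 4 or 5 gastrointestinal", thrombocytopenia of grade 4 or 5, and grade 4 liver enzyme elevation lasting 5 days or more. Two further items cover any organ: (e), an adverse event that interrupts therapy for 2 weeks or more, and (f), a treatment-related grade 5 event. Events must be at least possibly related to SRT and fall within 30 days from the start of treatment. No item names the kidney or the spinal cord.

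Section 9.3 defines a DLT as any CTCAE v3 toxicity of grade 4 or above, in any organ. Two affected patients at a dose level stop escalation, and escalation may also be halted for review outside the formal rules. Section 5.6.3 refers the reader to 10.1, not 9.3, for the definition.

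Section 5.2.3 sets planning limits for kidney and spinal cord. Section 5.4.2 includes both among the risks of SRT: "spinal cord injury which could result in paralysis, kidney function abnormality".

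**The concern.** The escalation rules work by counting patients with a DLT among three or six, so one reclassified patient can change the dose decision. Here the classification of a grade 4 renal event depends on which section the team opens. Kidney is not incidental: it is one of three organs named under the primary objective, has its own planning limit and is a listed risk.

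Two teams following this protocol in good faith could treat the same cohort, see the same renal events and reach different decisions on whether the next level opens and which level is called the MTD.

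**Working it through.** **1. Follow one event through both sections.** Take an SRT-related grade 4 renal event, not fatal, within 30 days from the start of treatment.

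- Section 10.1, items (a) to (d): not a DLT, because no item is renal.
- Section 10.1, item (f): not a DLT, because the event is not grade 5.
- Section 10.1, item (e): a DLT only if therapy is interrupted for at least 2 weeks. Treatment is 5 fractions given within 2 weeks. Once the fifth is delivered there is no therapy left to interrupt, so (e) can hardly apply to the rest of the 30-day window.
- Section 9.3: a DLT.

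A grade 4 spinal cord event gives the same two answers.

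**2. Reproduce the plan's own operating figures.** Section 10.3 gives at least 68% for not escalating at a true DLT rate of 35%, and 66% for escalating at 20%. With at most 1 DLT in a fixed group of 6:

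- Not escalating at 35%: 1 − 0.65^6 − 6(0.35)(0.65^5) = 0.681.
- Escalating at 20%: 0.80^6 + 6(0.20)(0.80^5) = 0.655.

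Both stated figures are reproduced to within a point. They take the DLT rate as given, so they do not show which events make up that rate. The two-stage rule written in the Dose-escalation Rules gives 0.604 and 0.709 instead. That rule is used below because it is the one that would be applied.

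**3. Size of the ambiguity (illustration).** Escalation follows 0 of 3, or 1 of 3 and then 0 of 3:

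P(escalate) = (1−p)^3 + 3p(1−p)^5

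Let o be the rate of DLTs from the organs listed in 10.1 and r the rate of grade 4 renal events that 10.1 would not count. Both are assumptions, since the documents give neither. If renal events do not count, p = o. If they count and are independent of the others, p = 1 − (1−o)(1−r).

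Worked case, o = 5%:

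- Not counted, p = 0.05: 0.95^3 + 3(0.05)(0.95^5) = 0.8574 + 0.1161 = 0.973.
- Counted, r = 1%, p = 0.0595: 0.9405^3 + 3(0.0595)(0.9405^5) = 0.8319 + 0.1314 = 0.963.
- Counted, r = 5%, p = 0.0975: 0.9025^3 + 3(0.0975)(0.9025^5) = 0.7351 + 0.1751 = 0.910.
- Counted, r = 10%, p = 0.145: 0.855^3 + 3(0.145)(0.855^5) = 0.6250 + 0.1988 = 0.824.

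The same formula at other background rates:

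| Listed-organ DLT rate | Renal not counted | Counted, r = 5% | Counted, r = 10% |
|---|---|---|---|
| 5% | 97.3% | 91.0% | 82.4% |
| 10% | 90.6% | 82.4% | 73.0% |
| 20% | 70.9% | 62.2% | 53.6% |

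Only the definition of DLT changes between columns; the escalation rule is held fixed.

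**4. Can right-kidney toxicity be scored?** Sections 7.1 and Appendix II schedule serum chemistry, which measures the two kidneys together. The planning limit in 5.2.3 also treats them jointly, on a total volume "defined as the sum of the left and right kidney volume". MRI is scheduled after SRT and images each kidney, but no side-specific test of renal function is planned.

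**The case against.** The strongest reply is that the protocol already protects against renal toxicity. Section 9.3 counts every grade 4 event, stops escalation at two per level and allows a discretionary halt. That stands, and it rules out a stronger reading that Section 10.1 alone might suggest: that grade 4 kidney toxicity cannot stop escalation. It does not remove the contradiction, because 5.6.3 sends the reader to 10.1, and the MTD definition and escalation tables also sit there. The discretionary halt has no threshold and only pauses escalation for review.

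A second reply is that a list of organs to record and a list of DLTs serve different purposes and need not match. That is fair. A reader might infer that gastric or platelet DLTs fall outside the primary endpoint because 1.1.1.1 does not name them. The documents do not support this: 1.1.1 is safety without an organ limit, 10.1 scores all toxicities, and 10.4 tables toxicity by dose level. The plan defines no single primary safety rate that such events could distort. Nor does one gastric or platelet DLT stop escalation: one in three leads to three more patients.

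Third, 5.4.2 places kidney and spinal cord effects among long-term effects and calls these less likely. This is a plausible reason for a 30-day list without a renal item, and it argues for small values of r. If that is the intention, 10.1 should say so and 9.3 should not say otherwise.

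**Conclusion.** The plan is wrong as written on one specific matter: Sections 9.3 and 10.1 disagree on whether an SRT-related, non-fatal grade 4 event counts as a DLT when its organ is not on the 10.1 list. Kidney is the most important case because 1.1.1.1 names it. The contradiction is textual and rests on no assumption.

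Its size does rest on assumptions. With 5% listed-organ DLTs and independent renal events, the two definitions differ by about 1 point in the chance of escalating at a renal rate of 1%, about 6 points at 5% and about 15 points at 10%. They do not differ if no such events occur. The documents support no particular value, and early rates may lie at the low end. The matter is worth correcting before enrolment because the rule governs dose decisions in very small cohorts and the correction is cheap.

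The organ wording in 1.1.1.1 and the abstract is a minor, separate matter. It is narrower than the scope of 10.1 and 10.4, and the word right asks for a distinction that the scheduled blood tests cannot make.

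**What to change.** Reconcile Sections 5.6.3, 9.3 and 10.1 into one DLT definition, stated once and cited elsewhere. It should say for each organ named in 1.1.1.1, and for organs such as the spinal cord that the 10.1 list omits, whether a grade 4 event counts. Which rule to adopt is for the investigators; the two passages cannot both stand. Editing 10.1 alone would not be enough, because an express statement there that renal events do not count would still contradict 9.3.

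As minor wording, align 1.1.1.1 and the abstract with the all-toxicity scope of 10.1 and 10.4, keeping named organs as organs of interest if wished, and refer to kidney function instead of the right kidney.

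The cost is text only. Serum chemistry is already scheduled, and the maximum of 28 patients does not change. If the investigators decide that renal events count, escalation becomes less likely when such events occur, by the amounts shown above for the assumed rates.

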## 6.3 Tumor Response

6.3.1 Measurable Disease Response: CTEP's RECIST guidelines will be followed. A quick reference to the RECIST guidelines can be downloaded at the following URL: <http://ctep.info.nih.gov/Policies/WordDocs/RCSTF.PH2TEMPF.doc>. (Appendix III)

Patients enrolled in this study must have a measurable HCC which is defined as lesions that can be accurately measured in at least one dimension: [longest diameter to be recorded] on the CT scan or MRI scan.

The same method of assessment & the same technique should be used to characterize each identified & reported lesion at baseline & during follow-up.

Parameters to Measure Response Outcome:	
1	Clinical examination
2	CT scan
3	MRI scan
4	AFP

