### 6.3.2 Response criteria

6.3.2.1 Taking into account the measurement of the longest diameter only for those lesions with size response, response criteria are defined as:

Complete Response (CR): the disappearance of a lesion.

Near Complete Response (NCR): at least an 80% decrease in the longest diameter of a lesion, taking as reference the longest diameter recorded since the treatment started.

Partial Response (PR): at least a 30% decrease in the longest diameter of a lesion, taking as reference the longest diameter recorded since the treatment started.

Progressive Disease (PD): at least a 25% increase in the longest diameter of a lesion, taking as reference the longest diameter recorded since the treatment started.

Stable Disease (SD): neither sufficient shrinkage to qualify for partial response nor sufficient increase to qualify for progressive disease, taking as reference the longest diameter since the treatment started.

6.3.2.2 The criteria used to determine the objective tumor response for those lesions without size response:

Complete Response (CR): the normalization of AFP level.

Partial Response (PR): at least a 25% decrease in the AFP level.

Progressive Disease (PD): the maintenance of AFP level above the normal limits

In some circumstances, it may be difficult to distinguish residual disease from the radiation induced necrotic tissue. When the evaluation of complete response depends on the normalization of AFP level, it is recommended that the residual lesion be investigated (fine-needle aspiration/biopsy) before confirming the complete response status.)

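### The AFP partial-response rule in 6.3.2.2 has no raised-baseline condition and conflicts with Appendix III; as a lesser point, MRI intensity change has no defined reference scale

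*Combined protocol and SAP*

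**What the plan says.** Objective 1.2.2 in Section 1.0 lists three percentages under objective tumour response: "Report the percentage of tumor size change on CT", "Report the percentage of intensity change on MRI" and "Report the percentage of change in AFP". None carries a condition on the baseline value.

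Section 6.3.2.1 defines response by the longest diameter. Section 6.3.2.2 then adds AFP, introduced as "The criteria used to determine the objective tumor response for those lesions without size response". Its categories are "Complete Response (CR): the normalization of AFP level", "Partial Response (PR): at least a 25% decrease in the AFP level", and progressive disease when AFP stays above normal. It gives no stable category.

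Sections 3.1 and 3.2 contain no AFP criterion; the diagnosis rests on tissue. Section 6.3.1 adopts RECIST as set out in Appendix III, whose measurement section says that response may not be assessed from tumour markers alone. The only rule bearing on how MRI signal is compared is also in 6.3.1: "The same method of assessment & the same technique should be used to characterize each identified & reported lesion", at baseline and follow-up.

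Section 10.4 plans radiological CR and PR rates at the MTD with 90% exact binomial intervals. Section 7.1 and Appendix II both schedule AFP before SRT and at 1 and 3 months after it.

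**The concern.** A percentage fall in AFP says something about tumour only if the tumour was raising AFP to begin with. If the value was normal before treatment and is still normal afterwards, a 25% fall may be nothing more than assay and biological variation, yet 6.3.2.2 turns it into a partial response. The rule is also one-sided for such a patient: the AFP progression label is out of reach and no stable label exists.

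What is at stake is the secondary response objective. Only 10 patients are added at the MTD, so one or two spurious partial responses would be visible in any rate that included them. The plan does not say whether AFP-based responses enter the rate in 10.4.

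The MRI figure raises a smaller version of the same question. With no sequence, contrast phase, region, reference tissue or normalisation specified, the reported percentage can mix scan-to-scan scaling with tumour change.

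**Working it through.** The plan gives no error rate, power or variability for AFP or MRI intensity, so there is no stated figure to reproduce.

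**1. Is a raised baseline required anywhere?** Sections 3.1 and 3.2: no. Objective 1.2.2.3: no. The PR line of 6.3.2.2: no. Appendix III mentions markers that start above normal, but only as a condition for complete clinical response once all lesions have disappeared.

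**2. Which AFP labels can a never-raised patient receive under 6.3.2.2?**

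| Label | Available? |
|---|---|
| PR | Yes, after any fall of 25% or more |
| CR | Not on the natural reading of normalisation, which implies a raised start; the text does not exclude it |
| SD | Not defined for AFP |
| PD | No; AFP would have to be above normal |

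Example, assuming an upper limit of 10: a change from 8 to 6 is (6 − 8)/8 = −25%. Both values are normal, and the rule gives PR.

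**3. How often would variation alone do this?** Assume log-normal within-patient variation with coefficient of variation c and no true change. Then s = √ln(1 + c²), the log ratio of follow-up to baseline has SD √2·s, and P(fall ≥ 25%) = Φ(ln 0.75 / (√2·s)), with ln 0.75 = −0.288.

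| Assumed CV | √2·s | P at one visit |
|---|---|---|
| 5% | 0.071 | <0.1% |
| 10% | 0.141 | 2.1% |
| 15% | 0.211 | 8.6% |
| 20% | 0.280 | 15.2% |
| 30% | 0.415 | 24.4% |

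The formula contains no baseline level. At the same CV these probabilities apply equally to patients with raised AFP.

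**4. Scale in patients.** Assume 16 patients at the MTD (6 from escalation plus 10 added), 20% to 50% of them with normal AFP (3.2 to 8.0 patients), and no size response in any of these. Expected spurious PRs at one visit are:
- CV 5%: effectively zero
- CV 10%: 3.2 × 0.021 to 8 × 0.021, or about 0.1 to 0.2
- CV 20%: 3.2 × 0.152 to 8 × 0.152, or about 0.5 to 1.2
- CV 30%: 3.2 × 0.244 to 8 × 0.244, or about 0.8 to 2.0

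**5. Internal conflict.** Section 6.3.1 adopts Appendix III, which bars response on markers alone. Section 6.3.2.2 assigns CR and PR on AFP alone. Both cannot govern. This needs no assumption about variability.

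**6. MRI.** If overall signal is scaled by a factor g between scans and the lesion is unchanged, the apparent change is (g − 1) × 100%: −20% for g = 0.8 and +25% for g = 1.25. A ratio of lesion to reference tissue on the same sequence has g in numerator and denominator, so it changes by 0%. Every category in 6.3.2 uses longest diameter or AFP; none uses intensity.

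**The case against.** The best defence is that the plan already contains the damage. Longest diameter comes first, AFP is used only where size has not responded, the rate in 10.4 is radiological, and Appendix III would by itself stop an 8-to-6 fall from being called a response. The AFP lines for CR and PD also presuppose a raised start. These are secondary measures in a phase I study of at most 28 patients and do not touch escalation, the MTD or the sample size.

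Much of this stands and limits the consequence. It does not remove the defect. The PR line carries no such presupposition, 6.3.2.2 and Appendix III contradict each other, and 10.4 does not expressly exclude AFP-based responses, while the Abstract and 6.3.1 list AFP among the means of assessing response.

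Four stronger readings are tempting and not supported:
- **MRI scaling could pass for response.** It cannot create a response or progression label, because no category uses intensity.
- **AFP change is uninterpretable throughout.** It remains meaningful in patients with a raised baseline.
- **MRI and AFP carry the response objective**, since the schedules, as the tables read, show no CT after treatment. Section 6.3.1 allows the longest diameter to be taken on MRI, so size response can still be assessed.
- **The probabilities show a hazard peculiar to normal-AFP patients.** They do not; they depend only on the assumed CV. They also move with the counting rule: a fall at either of two visits gives 3.8% at CV 10% and 37.2% at CV 30% (simulated, shared baseline), while a fall at both gives 0.4% and about 12%. Appendix III asks for confirmation of changes in tumour measurements, and its reach to AFP is unclear.

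**Conclusion.** The AFP point holds on the text. A patient with AFP normal throughout can be scored PR under 6.3.2.2 and can never be scored AFP-progressive, and the rule conflicts with the RECIST appendix that the protocol adopts. What is wrong with these patients is that the label has no tumour meaning; their false-fall rate need not be higher than anyone else's.

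The frequency cannot be fixed from the documents. At one visit it runs from below 0.1% at an assumed CV of 5% to about 24% at 30%, so it may be negligible or may amount to one or two patients at the MTD. The definitional fault and the contradiction stand at any CV.

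The MRI point is lesser: the measure is undefined and open to scaling, but only a descriptive percentage is affected. Neither point bears on safety conclusions or dose escalation.

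**What to change.** - **6.3.2.2 and 1.2.2.3:** apply the AFP categories and the AFP percentage-change summary only to patients above the upper normal limit at the last AFP value before SRT. List normal-AFP patients separately, with no AFP category.
- **6.3.2.2, Appendix III and 10.4:** report AFP response as a separate result and state that it does not enter the radiological CR/PR rate. That removes the conflict.
- **1.2.2.2:** report the change in the ratio of lesion signal to reference-tissue signal on the same named sequence, with the reference outside the irradiated liver, from the last MRI before SRT.

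Both schedules include AFP and MRI before and after SRT, so the last pre-SRT value exists under either and no extra test is needed. The cost is a smaller AFP summary and one reference-region reading per MRI.

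The restriction makes false AFP responses among never-raised patients zero by construction. It does not lower the false-fall rate in the patients retained. It also leaves an overlap in which a raised value that falls by 25% but stays above normal meets both PR and PD; an order of precedence should be stated in the same edit.
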